4.2.3 Feasibility counts

A feasibility count between 2015 and 2023 indicates approximately 1.7million A&G requests for 975,000 individuals.

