4.2.5 Sample size considerations

The feasibility count of 975,000 individuals gives an estimated mean of 108,000 per annum over the nine years of the study. Assuming an annual denominator population of 14 million (and hence prevalence of A&G of approximately 800/100,000), then per annum 95% confidence limits for the prevalence of A&G will be \pm 5/100,000. For assessing percentage of A&Gs which result in a referral, assuming an estimate of 50%, then per annum 95% confidence limits will be \pm 0.3% overall and \pm 3% for a lowest covariate (e.g., ethnicity group) category prevalence of 1%.

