4.3 DATA / STATISTICAL ANALYSIS

We will determine the annual total number of A&G and total number of routine direct referrals from 2015 to 2023. Annual prevalence will then be defined as the total number of patients with i) an A&G and ii) a routine referral code recorded within each calendar year, divided by the total registered population at the start of each calendar year and expressed per 100,000 persons. Annual incidence will be defined (as in our previous incidence studies) as the total number of patients with i) A&G and ii) routine referral codes recorded within each calendar year who have no recorded A&G or routine referral codes in the previous 24 months, divided by the total registered population with at least 24 months registration at the start of each calendar year, and expressed per 100,000 persons. We will determine prevalence and incidence overall, and stratified by age and sex.

Patterns of A&G use (number, prevalence, incidence) will also be described across specialties and type of health condition, and by neighbourhood deprivation, ethnicity, CCG, and geographical region to assess if any change over time in consultation incidence and prevalence varies by these characteristics. We will produce caterpillar plots to show variation by geographical region and CCG. We will repeat for quarterly incidence and prevalence of A&G (up to date of most recent CPRD Aurum build). We will use joinpoint regression analysis and segmented regression on the annual and quarterly prevalence and incidence to determine impact of the COVID pandemic [2020/2021] and changes in policy on A&G.

Within those with A&G we will derive the percentage with a recorded referral in the 122 days (4 months) i) before and ii) after A&G record and compare these over time, and by the covariates (excluding those with less than four months of follow-up), descriptively and by using binary logistic regression. We will repeat for the sensitivity analysis of 12 months. We will descriptively compare trends in incidence and prevalence of A&G and routine direct referrals with publicly available data on trends on e-referrals from https://digital.nhs.uk/dashboards/ers-open-data which currently covers the period October 2019 to March 2024.

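### The WP1a logistic regression and the precision in 4.2.5 make no allowance for clustering of patients within practices, and the unit of analysis is worded inconsistently

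*Protocol*

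**What the plan says.** Protocol 4.3 derives the percentage with a recorded referral in the 122 days before and after A&G. It compares these percentages over time and by the covariates "descriptively and by using binary logistic regression". The covariates in 4.2.8 are age, sex, geographical region, CCG pseudonym, ethnicity and deprivation. General practice is not among them, and neither section names a random effect, a GEE or a cluster-robust variance. Section 4.3 also says "We will produce caterpillar plots to show variation by geographical region and CCG".

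On precision, 4.2.5 starts from individuals: "The feasibility count of 975,000 individuals gives an estimated mean of 108,000 per annum over the nine years of the study". For prevalence it takes "Assuming an annual denominator population of 14 million" and a "prevalence of A&G of approximately 800/100,000", and gives ±5 per 100,000. For the referral percentage, "assuming an estimate of 50%, then per annum 95% confidence limits will be" ±0.3% overall and ±3% in a covariate category of 1% prevalence. No design effect is mentioned.

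The unit is not fixed. Section 4.2.5 speaks of A&Gs ("For assessing percentage of A&Gs which result in a referral, assuming an estimate of 50" per cent), and 4.2.8 speaks of A&G events, with the referral window counted from a request date. Section 4.3 takes the percentage among those who have an A&G, which reads as patients. The two readings differ, because 4.2.3 reports "approximately 1.7million A&G requests for 975,000 individuals".

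**The concern.** Patients are nested in practices, and practices in CCGs and regions. Referral habits and use of local A&G services plausibly differ between practices, and WP1a exists to describe variation in use (4.1). Region and CCG are the same, or nearly the same, for all patients of a practice. The effective sample size for those contrasts is therefore governed by the number of practices as well as the number of patients. A logistic model that takes patients as independent would give intervals for region and CCG that are too narrow. Chance variation between practices could then look like a difference between areas. The protocol requests CCG to identify potential inequities in practice (4.2.6), and a report of the mapping exercise is to go to policy makers and commissioners by month 12 (10.1.2), so the intervals on these contrasts matter.

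The unclear unit adds a second layer. If the model is run on A&G records, repeat records from the same person are correlated as well.

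**Working it through.** **Inputs from the protocol.** 975,000 individuals over nine years, taken as 108,000 a year; 1.7 million requests; annual denominator 14 million; prevalence about 800 per 100,000; referral percentage 50%; 95% confidence.

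**Step 1: reproduce the stated figures.** Half-width = 1.96 × √(p(1−p)/n).
- Prevalence: p = 0.008, n = 14,000,000 gives 4.67 per 100,000 (stated 5).
- Referral percentage overall: p = 0.5, n = 108,000 gives 0.298 points (stated 0.3).
- Category of 1%: n = 1,080 gives 2.98 points (stated 3).

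All three agree with simple binomial limits and a design effect of 1.

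**Step 2: which unit did 4.2.5 use?** Records would be 1,700,000/9 = 188,889 a year, giving 0.225 points overall and 2.25 points in the 1% category. Neither matches. The stated precision counts individuals.

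**Step 3: allow for practice clustering.** Design effect DE = 1 + (m − 1) × ICC, and the half-width is multiplied by √DE. The protocol gives neither the number of practices nor an ICC. Assume 1,200 to 1,500 practices, so m = 108,000/1,200 = 90 down to 108,000/1,500 = 72 A&G patients per practice per year, and an ICC of 0.01 to 0.05.

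| Practices | m | ICC | DE | Half-width (points) |
|---|---|---|---|---|
| 1,500 | 72 | 0.01 | 1.71 | 0.39 |
| 1,200 | 90 | 0.01 | 1.89 | 0.41 |
| 1,500 | 72 | 0.05 | 4.55 | 0.64 |
| 1,200 | 90 | 0.05 | 5.45 | 0.70 |

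A wider range (1,000 to 2,000 practices, ICC 0.01 to 0.10) gives 0.37 to 1.02 points.

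**Step 4: the 1% category.** 1,080 patients over 1,200 to 1,500 practices is fewer than one per practice if they are evenly spread. DE is then about 1 and ±3 points stands. It widens only if the group is concentrated in few practices.

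**Step 5: contrasts constant within practice.** The full design effect applies here. A nominal 5% test with unadjusted errors has an effective critical value of 1.96/√1.71 = 1.50 to 1.96/√5.45 = 0.84. That is a false-positive rate of about 13% to 40%. This uses one year of data. Pooling nine years gives 975,000/1,500 = 650 to 975,000/1,200 = 812 patients per practice, so the inflation is larger if practice habits persist.

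**Step 6: prevalence.** With 1,000 to 2,000 practices and an assumed ICC of 0.0005 to 0.001, DE is 4.5 to 15.0 and ±4.67 becomes about ±10 to ±18 per 100,000. This matters only for inference beyond the observed registered population.

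**Step 7: repeats within patient, if records are modelled.** 1,700,000/975,000 = 1.74 requests per person over the whole period. With equal numbers per person and an assumed within-person ICC of 0.3 to 0.8, DE = 1 + 0.74 × ICC = 1.22 to 1.59. True standard errors are then 1.11 to 1.26 times the unadjusted ones.

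**The case against.** The strongest reply is that binary logistic regression names an outcome model and not a variance estimator. Clustered errors or a random intercept would be compatible with the wording, and such detail is often left to an SAP, which was not available here. This stands as far as the wording goes: the protocol nowhere says that observations will be treated as independent. The right statement is that the intervals would be too narrow if nothing is done. It does not rescue 4.2.5, where the protocol itself fixes figures with a design effect of 1.

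Second, region and CCG are already covariates. CCG as a fixed effect absorbs differences in level between CCGs, but not the variation between practices inside a CCG. That variation is what determines the uncertainty of the CCG estimates themselves. If CCGs are nested in regions, region effects are also not separately estimable beside CCG fixed effects.

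Third, WP1a is labelled descriptive and hypothesis generating, disclaims causal conclusions about locality, and has no decision rule that depends on these intervals. That limits the consequence, but published intervals on area differences should still be valid.

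A reader might also infer four stronger points that the protocol does not support:
- That the stated precision counts repeat records as independent. It does not, because it reproduces on individuals. Even fully correlated records would return 0.298 points.
- That year and deprivation contrasts suffer most. Year varies within practices, where ignoring a stable practice effect tends to make standard errors too large. Deprivation is specified at patient level in 4.2.6.
- That the caterpillar plots use raw rates. The text does not say what they will show.
- That the WP2 models share the fault. Nothing in the WP2 text shows this, and WP2 is still to be designed.

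**Conclusion.** The point holds in a limited form. The model in 4.3, run as written, makes no allowance for practice-level variation, and the precision in 4.2.5 is simple binomial on individuals. Intervals for region and CCG would be too narrow unless adjusted. The unit of analysis is inconsistent between 4.2.5, 4.2.8 and 4.3, and a record-level model without patient clustering would understate standard errors as well.

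For the overall referral percentage the size is modest: about ±0.4 to ±0.7 points in place of ±0.3. The 1% category hardly changes if it is evenly spread. The effect is more serious for region and CCG contrasts, where the full design effect of about 1.7 to 5.5 applies. All these magnitudes rest on assumed practice numbers and ICCs. The absence of a design effect in 4.2.5 and the inconsistent unit do not depend on those assumptions.

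**What to change.** 1. In 4.3, state that the logistic models use practice-clustered robust standard errors, or a practice random intercept nested in CCG.
2. Fix the unit as one index A&G per patient per period, and use the same term in 4.2.5, 4.2.8 and 4.3. If records are kept as the unit, make sure the clustering also covers repeat records within patients.
3. In 4.2.5, restate the overall ±0.3% with a design-effect range and its assumptions, for example about ±0.4 to ±0.7 points under 1,200 to 1,500 practices and an ICC of 0.01 to 0.05. Note that ±5 per 100,000 assumes no clustering.

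No change of design is needed. The cost is revised wording, more computing time and slightly less favourable stated precision.

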4.3.1 Plan for addressing confounding

This is a descriptive/exploratory and hypothesis generating study. We will acknowledge in dissemination unmeasured factors like symptom or disease severity may confound associations between the covariates and A&G and in referral following an A&G.

NIHR 158681BADGER			
Protocol Version 2.0 18/06/2024	CPMS: 58336	IRAS No: 333799	CPRD ID: 24_004022

4.3.2 Plans for addressing missing data

We will assume that if no code for A&G or referral is entered, it did not occur. It is possible the quality of recording has improved in recent years and will discuss this as a limitation in dissemination, but we do not expect bias in recording by the covariates. Not everyone will have an ethnicity recorded, and we will use a "Not recorded" category.

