To derive the comparative prevalence and incidence of elective referrals, direct routine referrals will be determined using codes with a term indicating a referral and defined by consensus of study team to indicate a routine referral to a specialty (i.e. not fast track or referral with an intention to admit / emergency referral). To ascertain A&G events which result in a direct referral, we will determine

NIHR 158681BADGER			
Protocol Version 2.0 18/06/2024	CPMS: 58336	IRAS No: 333799	CPRD ID: 24_004022

referrals within 122 days (4 months) after date of an A&G request. These will be defined as i) a direct referral code defined as above and by ii) linking events in the Referrals table to the Observation table and determining duration of time between the linked observation event and the A&G request date. We will also determine referrals within 122 days (4 months) before an A&G request to see how often A&G requests follow a referral request. As a sensitivity analysis we will repeat for 365 days (12 months) either side of the A&G request date. Code lists for A&G have been derived and used in our CPRD feasibility study (FS_002830). The draft code list for direct referral has also been developed. These code lists are included in the appendix.

Covariates:

- 1) Age at date of A&G request (categorised)
- 2) Sex
- 3) Geographical region
- 4) CCG pseudonym
- 5) Ethnicity group
- 6) Deprivation (based on IMD quintiles)

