4.3.3 Limitations of the study design

As above, it is possible recording of A&G and referral has improved over time.

As an observational study, there is the potential for unmeasured confounding factors to affect the findings. It will not be possible to conclude any causal relationship between variations in locality or socio-demographic characteristics for A&G versus usual referrals due to our study being both exploratory and descriptive. Misclassification of cases, exposures, and covariates is possible but expected to occur at random and so not introduce a significant degree of bias.

There may be other locality-dependent portals available for primary care clinicians to access specialist input without requiring a formal referral, such as teledermatology services and applications such as Consultant Connect, which facilitate telephone contact with the consultant/specialist and may not be coded by the GP. The consequence of this is that there may be missed episodes of A&G, but we believe this to be the minority of cases or at the more urgent end of the spectrum of clinical presentations rather than our focus on elective care.

5 WORK PACKAGE 2 a&b (QUANTITATIVE)

This section of the protocol relates to Work Package 2 a&b and will be designed iteratively as findings from WP 1b and our work with our PPIE and stakeholders emerge. Permissions will be sought from the RDG Secretariat via the electronic Research Application Portal.

Study Title: Determining outcomes of the use of Advice and Guidance: a cohort study

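### The protocol expects no recording bias by CCG or region, yet says uncoded A&G portals depend on locality, so recording differences can appear as variation in A&G use

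*Protocol*

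**What the plan says.** Four parts of the WP1a plan bear on this.

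- **Denominator (Protocol 4.3).** Patients with an A&G code in the year are "divided by the total registered population at the start of each calendar year and expressed per 100,000 persons". For incidence the count is "divided by the total registered population with at least 24 months registration at the start of each calendar year". Neither is limited to practices that record A&G.
- **No code (4.3.2).** "We will assume that if no code for A&G or referral is entered, it did not occur". On change over time: "It is possible the quality of recording has improved in recent years and will discuss this as a limitation in dissemination". On everything else: "we do not expect bias in recording by the covariates".
- **Covariates (4.2.8).** The list includes geographical region and "4) CCG pseudonym".
- **Limitations (4.3.3).** "There may be other locality-dependent portals available for primary care clinicians to access specialist input". The section adds that GPs may not code these contacts and that A&G episodes may be missed. It believes these are a minority or the more urgent cases, and it expects misclassification to be random.

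The rates feed joinpoint and segmented regression over time and caterpillar plots by region and CCG (4.3). Section 4.2.6 requests the CCG identifier so that variation between localities can point to possible inequity.

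**The concern.** If the chance that an A&G contact leaves a code depends on locality, recording is biased by a covariate. That is what 4.3.2 says is not expected and what 4.3.3 describes. With the whole registered population underneath, an uncoded contact lowers the rate exactly as a contact that never happened would. A CCG that uses another portal then looks like a CCG with less A&G, and spreading code use can add to an upward trend.

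These contrasts are main outputs of WP1a. Growth over time is its first aim (4.1), CCG variation is to be examined for inequity (4.2.6), and the mapping report is due to policy makers and commissioners by month 12 (10.1.2).

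**Working it through.** **1. The plan's own precision figures (4.2.5).**
Inputs: 975,000 individuals, nine years, annual denominator 14 million.

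- 975,000 / 9 = 108,333 per year. 108,333 / 14,000,000 = 774 per 100,000, which the plan rounds to about 800.
- Half-width = 1.96 × √(p(1 − p)/n). With p = 0.008 and n = 14,000,000 this is ±4.67 per 100,000 (plan: ±5).
- With p = 0.5 and n = 108,000 it is ±0.298% (plan: ±0.3%). With n = 1,080 it is ±2.98% (plan: ±3%).

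The figures reproduce. They cover sampling error only.

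**2. Effect of incomplete capture on the trend.**
Observed rate = true rate × c, where c is the share of A&G that leaves a code. The protocol gives no value of c, so every c below is an assumption. The true rate is held at 800 per 100,000.

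| c, start → end | Observed rate | Apparent change |
|---|---|---|
| 80% → 90% | 640 → 720 | +12.5% |
| 70% → 90% | 560 → 720 | +29% |
| 50% → 90% | 400 → 720 | +80% |
| 30% → 90% | 240 → 720 | +200% |

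The first row is a shift of 80 per 100,000, or 80 / 4.67 ≈ 17 of the plan's single-year half-widths. A capture change equal to 4.67 / 800 ≈ 0.6% of the true rate already matches one half-width. Narrow intervals therefore give no protection against this error.

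**3. Effect on CCG contrasts.**
The number of CCGs is not stated. Assume 50, 100 or 200 of equal size.

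| CCGs | People each | Half-width per 100,000 |
|---|---|---|
| 50 | 280,000 | ±33 |
| 100 | 140,000 | ±47 |
| 200 | 70,000 | ±66 |

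Sending 5% of A&G through uncoded routes shifts a CCG by 0.05 × 800 = 40, which exceeds the half-width only in the 50-CCG case. Sending 10% shifts it by 80 and 20% by 160, beyond the half-width in all three.

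**4. What a restricted denominator can and cannot do.**
If the uncaptured activity sits in whole practices that record nothing, and the true rate is the same in all practices, removing those practices restores 800 per 100,000. The half-width is then ±4.9 (90% of the population kept) to ±8.5 (30% kept).

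Partial loss is not corrected. An assumed practice of 7,000 patients expects 7,000 × 0.00774 ≈ 54 coded patients a year. At one-tenth capture it still expects about 5.4, and the Poisson chance of no code at all is e^(−5.4) ≈ 0.5%. Such a practice would almost always count as recording.

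**The case against.** **The plan has more than a caveat.** Section 4.2.8 says an e-RS activity cannot be saved and exited without a code, which makes wholesale non-coding on that route unlikely. Section 4.3 compares the trends with public e-RS data. Both are real safeguards, with limits. Forced coding covers the e-RS route only, and 4.2.8 itself falls back on a code for advice received where no request code is found. The external comparison is descriptive, starts in October 2019 although the series starts in 2015, is stated for trends rather than CCGs, and concerns e-referrals rather than other portals.

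**The study is descriptive and limits its claims.** It is labelled exploratory, 4.3.3 rules out causal conclusions about locality, and 4.2.6 speaks only of possible inequity. Section 1.1.2 makes the two elective e-RS options the focus. This stands, and it lowers the weight of the point. It does not reconcile 4.3.2 with 4.3.3, and 1.1.2 also counts voice calls as A&G, so a telephone portal falls within the protocol's own definition.

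**A sensitivity analysis can wait for the SAP.** That is fair for its detail. The contradicted assumption, however, is fixed in the protocol text.

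**Stronger readings.** A reader might infer that any reported growth or CCG variation will be a recording artefact. The documents give no capture share, so they do not support that. A reader might extend the point to age, sex, ethnicity and deprivation, but nothing in the protocol suggests that recording differs on those. A reader might also conclude that only a rise within recording practices is true growth. That is wrong: practices taking up A&G for the first time is growth too, and 1.2 says the pandemic accelerated its use.

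**Conclusion.** The point holds as an inconsistency with practical consequences. The expectation of unbiased recording in 4.3.2, and of random misclassification in 4.3.3, cannot stand for CCG and region beside the locality-dependent portals in 4.3.3. With an all-registered denominator and absence of a code read as absence of A&G, differences in coding or portal use can appear as CCG or regional variation or as part of the trend.

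The size is unknown. The illustrations rest on assumed capture shares, equal-sized CCGs and a constant true rate. They show that modest differences in capture would exceed the plan's sampling error, not that such differences exist. For time, the plan already admits that recording may have improved. The gap there is that the analysis does not separate the spread of recording from the rate within recording practices. There is no contradicted statement about time to withdraw.

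**What to change.** 1. **In 4.3.2 and 4.3.3**, withdraw the no-bias and at-random expectations for CCG and region. State that a low CCG or regional rate may reflect uncoded portals and is not to be read as inequity on its own.
2. **In 4.3**, keep the all-registered rate as the main result. Add a sensitivity analysis restricted to practices with at least one A&G code in the calendar year, or in the preceding four quarters for the quarterly series. For the trend and the CCG and region plots, report side by side the share of the population in recording practices and the rate within them.
3. **Interpretation.** Do not make the within-practice rate the sole test of growth. A rising share may be true adoption or uptake of the code, and the data cannot tell these apart.

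The cost is a practice-period flag and one repeated analysis. The restricted rate conditions on having a code, may drop practices that truly made no A&G requests, and does not correct partial diversion or under-coding within a recording practice. It therefore belongs beside the main rate and should not replace it.
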